# **FORBIUS**

- baseline; or c) decreased by 20 msec under baseline.
- 14. Ophthalmology Examination: To include slit lamp evaluation, tests to evaluate corneal integrity, and visual acuity assessment. End of C2 and EOT may be combined if patient discontinues treatment at End of C2
- 15. MUGA Scan or Echocardiogram: For measurement of LVEF; to be performed ONLY in patients with a history of CHF, individual patients should be followed with the same testing procedure throughout the study.
- 16. Pulmonary Function Tests: To include spirometry and diffusing capacity (DLCO) to assess for evidence of pulmonary fibrosis (spirometry assessments are to include but are not limited to: forced vital capacity [FVC], forced expiratory volume in 1 second [FEV1], forced expiratory flow 25% to 75% [FEF25-75], functional residual capacity [FRC], residual volume [RV], and total lung capacity [TLC])
- 17. EGFR status determination/documentation of EGFR positivity by IHC:
  - Phase 1a: Optional (Local or Central\*)
  - Phase 2a: Required (Central Lab\*); tumor must be EGFR-positive for patient to be eligible for enrollment
  - \*The trial site will prescreen patients for EGFR Tumor Status Determination before entering patients into screening for the treatment portion of the trial. The site should use a separate prescreening informed consent form. Prescreening may be performed outside the 28 (+ 2) day screening period to allow adequate turnaround time for receipt of results, provided separate informed consent has been obtained.
- 18. Tumor Marker Measurement (Phase 1a only): As indicated by tumor type.
- 19. Imaging for Assessment of Disease (and Pulmonary Status) (e.g., diagnostic imaging / marker lesion measurements, etc.; as indicated by tumor type, imaging of the chest imaging required with each evaluation (for disease evaluation where indicated, and to assess for evidence of pulmonary fibrosis): Follow with the same procedure(s) throughout; no further disease assessments required after documented PD and/or initiation of another therapeutic intervention; duration of OR to be measured from date initial response is observed to date PD is observed; for PR or CR, tumor measurement changes must be confirmed no less than 4 weeks after criteria for response are met; for SD, follow-up measurements must meet the SD criteria at least once after study entry at a minimal interval of not less than 8 weeks. Imaging studies documenting response must be available for review by the Sponsor (or designee).
- 20. Response Assessment: To be assessed by the Investigator according to RECIST v1.1
- 21. PK Sampling (Central Lab): Whole blood (~5 mL at each timepoint) will be collected for serum acquisition. In the event that a collected serum sample is inadequate or insufficient for PK analysis, the analysis of PK can be done using an anti-drug antibody (ADA) serum sample from the same time point, if available. Residual sample material may be used for biomarker assessments. See Laboratory Manual (or other similar document) for details regarding collection, handling, and shipping. PK sampling times may be adjusted according to early trial results in order to optimize evaluation.
- 22. Tumor for Exploratory Studies (Central Lab): For assessment of tumor EGFR-expression by FISH (or similar assay) and other potential biomarkers. Directions for submitting blocks or pre-cut slides to be provided by the Sponsor (or designee) in the Laboratory Manual or other similar document.
  - Phase 1a: To be submitted if available.
  - Phase 2a: Required; to be performed in tumor tissue submitted for eligibility; if archival tissue is not available the patient must have primary or metastatic tumor sites(s) considered safely accessible for biopsy, and must be willing to undergo tumor biopsy
- 23. Blood for Exploratory Studies (Central Lab): Phase 2a; may be obtained for submission any time after confirmation of eligibility and study enrollment but prior to dosing on C1/D1

TABLE 8: PHARMACOKINETIC SAMPLING SCHEDULE See also TABLE 4													
Study Day	Phase 1a	Phase 2a	Allowance (+/-)	Reference									
CYCLE 1													
Day 1	SOI	SOI		Prior to SOI									
	EOI	EOI	5 min										
	2h		15 min	EOI									
	4h		15 min										
Day 2	24h		1h										
Day 4	At time of visit		1 day										
Day 8	At time of visit	At time of visit											
CYCLE 2													
Day 1	SOI	SOI		Prior to SOI									
	EOI		5 min	EOI									
Day 8	At time of visit												
POST-TREATMENT													
EOT	At time of visit	At time of visit											
1M FUP	At time of visit	At time of visit											
In the event of an IRR	At time of	At time of											
In the event of an IRR	event	event											
TOTAL SAMPLES	12	5											

SOI = Start of Infusion EOI = End of Infusion

PK samples for each additional cycle:

• Phase 1a: Day 1 (SOI, EOI)

• Phase 2a: Day 1 (SOI)

Day 1 (SOI, EOI) *Cycle 5 only*Day 8 (at time of visit) *Cycle 5 only* 

Actual collection times are to be recorded on the patient's eCRF or other equivalent sample collection log as authorized by the Sponsor (or designee).

Comprehensive collection of clinical samples is critical to the conduct of this study. In situations where collection of the 4h sample is logistically difficult due to clinic staff availability, an "end of day" sample may be obtained at the latest practical time. Such an option is available ONLY after previous discussion with and approval by the Sponsor.

	TABLE 9: MAXIMUM TOTAL BLOOD COLLECTION VOLUMES											
STUDY	Vol./	Screen	ing	Cycl	e 1	Cycle	2	EO	Γ	1M F	UP	TOTAL
ASSESSMENTS	sample (mL)	# of Samples	Vol. (mL)	VOLUME								
Phase 1a												
Hematology	5	1	5	3	15	2	10	1	5	1	5	40
Chemistries	10	1	10	3	30	2	20	1	10	1	10	80
Coagulation	5	1	5	3	15	2	10	1	5	1	5	40
Pregnancy Test	5	1	5	0		0		0		0		5
ADA Testing	5	0		1	5	1	5	1	5	1	5	20
Tumor Markers	5	1	5	0		1 (end)	5	1	5	1	5	20
PK Studies	5	0		7	35	3	15	1	5	1	5	60
Total Volume			30		100		65		35		35	265
Phase 2a												
Hematology	5	1	5	3	15	2	10	1	5	1	5	40
Chemistries	10	1	10	3	30	2	20	1	10	1	10	80
Coagulation	5	1	5	3	15	2	10	1	5	1	5	40
Pregnancy Test	5	1	5	0		0		0		0		5
ADA Testing	5	0		1	5	1	5	1	5	1	5	20
PK Studies	5	0		3	15	1	5	1	5	1	5	30
Exploratory Studies	20	1	20	0		0		1	20	0		40
Total Volume	•		45		80		50		50		30	255

Along with Screening, single days not detailed with maximum blood volume requirements > 20 mL:

- Phase 1a: Cycle 1/Day 1= 50mL, Day 4=25mL
- Phase 2a: Cycle 1/Day 1=35mL (55 mL if biomarker sample is drawn prior to dosing on C1/D1)

Blood volumes for each additional cycle: 50 mL, 60 mL for Cycle 5

If sites are able to perform hematology, serum chemistry, and coagulation studies with smaller volumes of blood per sample, they are encouraged to do so. Required PK, and ADA volumes are fixed and should not be reduced.

For the purpose of estimating a patient's total blood collection volume during study participation, maximum estimates are used. During a patient's study participation, the maximum amounts of venous blood that will be collected are listed above. Study duration is based on 6 weeks estimated average patient participation, i.e., an average of Cycle 1 (3 weeks) plus Cycle 2 (3 weeks).

An indwelling venous access device is required for PK blood sample collections on Day 1 of Cycle 1. When an indwelling catheter (or equivalent venous access) is utilized, a blood flush discard of up to 3 mL is to be done before drawing the first blood tube collected on the scheduled day/time for routine laboratory tests and PK samples. **Blood flush discard volumes ARE NOT included in volume calculations in table above and should be considered when summarizing actual blood collection volumes.** 

Given the Q3W dosing frequency, EOT and 1M FUP evaluations may be combined in those situations where scheduling coincides, provided a minimum of 30 days of post-dosing follow-up have been observed.

## In the event of an IRR:

If a patient should have an IRR associated with AVID100 administration, all attempts will be made to obtain blood samples as close to the onset of the event as possible for assessment of the presence of ADA and PK (to provide information on the nature of the infusion reaction). Blood volume for such collections is not included on this table; however, it is anticipated that a total of approximately 10 mL would be required; ADA (5 mL), PK (5 mL).

# **APPENDIX B**

# **Performance Status Evaluation**

	TABLE 10: MEASURES OF PERFORMANCE STATUS								
Percent	KARNOFSKY  Performance Status Description		Level	ECOG 					
100	Normal; no complaints, no evidence of disease		0	Normal activity					
90	Able to carry on normal activity; minor signs or symptoms of disease								
80	Normal activity with effort; some signs or symptoms of disease		1	Symptoms but ambulatory					
70	Cares for self; unable to carry on normal activity or do active work								
60	Requires occasional assistance but is able to care for most needs		2	In bed < 50% of time					
50	Requires considerable assistance and frequent medical care								
40	Disabled; requires special care and assistance		3	In bed > 50 % of time					
30	Severely disabled; hospitalization is indicated although death is not imminent								
20	Very sick; hospitalization is necessary		4	100 % bedridden					
10	Moribund; fatal processes progressing rapidly								
0	Death		5						

<sup>1Karnofsky DA, Abelman WH, Craver LF, Burchenal JH. The use of nitrogen mustards in the palliative treatment of carcinoma. *Cancer*. 1948;1:634-656.

<sup>2Oken M, Creech RH, Tormey DC, Horton J, Davis TE, McFadden E, Carbone PP. Toxicity and response criteria of the eastern cooperative oncology group. Am J Clin Oncol. (CCT) 1982; 5:649-655.

# **APPENDIX C**

# **New York Heart Association's Functional Criteria**

TABLE 11: NEW YORK HEART ASSOCIATION FUNCTIONAL CRITERIA					
Class I	No limitation of physical activity. Ordinary physical activity does not cause undue fatigue, palpitation, dyspnea, or anginal pain.				
Class II	Slight limitation of physical activity. Comfortable at rest, but ordinary physical activity results in fatigue, palpitation, dyspnea, or anginal pain.				
Class III	Marked limitation of physical activity. Comfortable at rest, but less than ordinary physical activity results in fatigue, palpitation, dyspnea, or anginal pain.				
Class IV	Unable to carry on any physical activity without discomfort. Symptoms of cardiac insufficiency or anginal syndrome may be present even at rest. If any physical activity is undertaken discomfort increases.				

The Criteria Committee of the New York Heart Association. Nomenclature and Criteria for Diagnosis of Diseases of the Heart and Great Vessels. 9th ed. Boston, Mass: Little, Brown & Co; 1994:253-256

# APPENDIX D

# **Adverse Event Grading Scale**

TABLE 12: CLINICAL ADVERSE EVENT GRADING							
Severity	CTCAE* Grade	Definition					
Mild	1	Awareness of symptom, but easily tolerated. Event is usually transient requiring no special treatment; does not interfere with usual status or activities					
Moderate	2	Event may be ameliorated by simple therapeutic measures; may interfere with usual activities					
Severe	3	Event results in temporary disability or incapacity; inability to perform usual activities; requires intervention					
Life-threatening	4	Event requires immediate intervention; need for emergency treatment; patients is at risk of death at the time of the event					
Fatal	5	Event resulting in the subsequent death of the patient					

Note: In those cases where further definition of an event is provided by the NCI Common Terminology Criteria for Adverse Events (CTCAE, v5.0), please refer to that document for grading and severity information.

\*< https://ctep.cancer.gov/protocolDevelopment/electronic\_applications/ctc.htm >

Protocol: AVID100-01 Advanced Epithelial Carcinomas

## APPENDIX E

# Clinical Adverse Events: Determining Relationship to Study Drug

## TABLE 13: CLINICAL ADVERSE EVENTS: DETERMINING RELATIONSHIP TO STUDY DRUG

## UNRELATED

This category applies to those AEs which, after careful medical consideration, are clearly felt to be due to extraneous causes (disease, environment, etc) that are unrelated to the administration of study drug.

## **UNLIKELY RELATED** (must have first 2)

This category applies to those AEs which, after careful medical consideration, are felt unlikely to be related to the administration of the study drug. The relationship of an AE to the study drug can be considered unlikely if:

- It does not follow a reasonable temporal sequence from administration of the drug.
- It could readily have been a result of the patient's clinical state, environmental or toxic factors, or other modes of therapy administered to the patient.
- It does not follow a known response pattern to the suspected drug.
- It does not reappear or worsen when the drug is readministered.

#### **POSSIBLY RELATED** (must have first 2)

This category applies to those AEs which, after careful medical consideration, are felt unlikely to be related to the administration of the study drug, but the possibility cannot be ruled out with certainty. The relationship of an AE to the study drug can be considered possible if:

- It follows a reasonable temporal sequence from administration of the drug.
- It could readily have been a result of the patient's clinical state, environmental or toxic factors, or other modes of therapy administered to the patient.
- It follows a known response pattern to the suspected drug.

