#### 6.8.3 Definition of DLT

Any of the following toxicities, if judged to be associated with study drug (i.e., possibly related, probably related, or related), will be considered a DLT for the purposes of this trial.

- 1. Evidence of pulmonary fibrosis, any grade (patient must be permanently discontinued)
- 2. Grade 3 non-hematologic toxicity regardless of duration, with the exceptions of:
  - Grade 3 nausea, vomiting, diarrhea, or fatigue lasting  $\leq$  2 days with best supportive care
  - Grade 3 asymptomatic electrolyte abnormalities that are not considered clinically significant by the Investigator and that are controlled with medical therapy
- 3. AST and/or ALT elevation  $> 3 \times \text{ULN}$  (or  $> 3 \times \text{baseline}$  if elevated at study entry as allowed by study eligibility criteria; see **Section 4.3.1** #7), with total bilirubin  $> 2 \times \text{ULN}$  without initial findings of cholestasis (i.e., no elevation in serum alkaline phosphatase [ALP]), that cannot be explained by other factors
- 4. Any Grade 4 non-hematologic toxicity with the exception of:
  - Grade 4 asymptomatic electrolyte abnormalities lasting < 7 days that are not considered clinically significant by the Investigator and that are controlled with medical therapy
- 5. Neutropenia that is:
  - ≥ Grade 3 and associated with fever (ANC < 1000 per mm³; temperature > 38.3°C [101°F] or a sustained temperature of ≥ 38 °C [100.4°F] for > 1 hour ) (i.e., febrile neutropenia)
  - Grade 4 and sustained (ANC < 500 per mm^3, duration > 5 days)
- 6. Thrombocytopenia that is:
  - Grade 3 with clinically significant hemorrhage or requirement for transfusion

- Grade 4 (platelets < 25,000 per mm^3)
- 7. Inability to complete Cycle 1 at the assigned dose (i.e., receipt of < 1 full planned dose of study drug plus 3 weeks of follow-up due to  $\geq$  Grade 3 toxicity)
- 8. Treatment delays > 2 weeks from the scheduled "next dose" due to ≥ Grade 3 toxicity Other toxicities may be considered a DLT as determined by the Investigator in conjunction with the Medical Monitor.

The above criteria will be used to make individual patient determinations regarding dose reductions, interruptions, or discontinuation throughout the course of the trial, but *only those DLTs occurring during Cycle 1* will be used to make decisions regarding cohort dose escalation and tolerability.

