#### 10.3.1 Information to be Provided for each AE

The following information will be provided for each AE term reported:

• Each event will be graded according to the CTCAE (v5.0) as to severity. For events not listed in the CTCAE, severity will be graded on a 5-point scale as mild, moderate, severe, life threatening, or fatal, which correspond to Grades 1, 2, 3, 4, and 5, respectively on the CTCAE (see **Appendix D**; Adverse Event Grading Scale).

- The date of onset as well as the duration of the event will be recorded (i.e., date of resolution).
- The method used to treat the AE, specifically, the action taken regarding the study drug will be provided (e.g., none, infusion temporarily interrupted, infusion prolonged, infusion stopped, dose reduced, dose schedule altered, dosing permanently discontinued).
- The outcome of the AE (e.g., ongoing, resolved, resolved with sequelae, fatal) will also be noted.
- The Investigator will attempt to assess the relationship of the event to study drug. Investigators are required to assess whether there is a reasonable possibility that the investigational drug caused or contributed to an AE. Determination of whether there is a reasonable possibility includes assessing temporal relationships, biologic plausibility, dechallenge/rechallenge information (if available), association (or lack of association) with underlying disease, and presence (or absence) of a more likely cause. The Investigator must attempt to determine if an AE is in some way related to the use of the study drug using a 5-point causality scale (i.e., unrelated, unlikely-related, possibly related, probably related, related) (see Appendix E; Clinical Adverse Events: Determining Relationship to Study Drug).

*Preexisting condition* (i.e., disorders present before the AE reporting period started and noted during the Screening period) should not be reported as an AE unless the condition worsens or episodes increase in frequency during the AE reporting period.

*Diagnostic and therapeutic procedures*, such as surgery, should not be reported as AEs. However, the medical condition for which the procedure was performed should be reported if it meets the definition of an AE. For example, acute appendicitis that begins during the AE reporting period should be reported as the AE and the resulting appendectomy should be noted as the intervention for the AE.

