## **PROBABLY RELATED** (must have first 3)

This category applies to those AEs which, after careful medical consideration, are felt with a high degree of certainty to be related to the administration of the study drug. The relationship of an AE to the study drug can be considered probable if:

- It follows a reasonable temporal sequence from administration of the drug.
- It could not be reasonably explained by the known characteristics of the patient's clinical state, environmental or toxic factors or other modes of therapy administered to the patient.
- It disappears or decreases upon cessation of drug or reduction in dose.\*
- It follows a known response pattern to the suspected drug.

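### Table 13 has no causality category for an event with plausible timing, no other cause and no usable dechallenge information, so it enters the DLT count only by discretion

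*Combined protocol and SAP*

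**What the plan says.** **How relatedness is used.** Under Section 6.8.3 a listed toxicity, "if judged to be associated with study drug (i.e., possibly related, probably related, or related), will be considered a DLT". The same section lets the investigator and the Medical Monitor call other toxicities DLTs. Section 6.6.3.3 re-evaluates the dose when at least 33.3% of an expansion cohort has a Cycle 1 DLT. Section 14.3 tabulates treatment-related AEs, Section 14.3.2.1 summarizes AEs by relatedness, and Section 14.1 combines Phase 2a data with Phase 1a patients at the same dose.

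**How relatedness is assigned.** Section 10.3.1 requires a "5-point causality scale (i.e., unrelated, unlikely-related, possibly related, probably related, related"), defined in Appendix E. The same bullet frames the question as whether there is a reasonable possibility that the drug caused or contributed to the event. It treats dechallenge and rechallenge information as an input only when it exists.

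**The compulsory items in Table 13:**
- *Unrelated*: no checklist, but the event must clearly come from an extraneous cause.
- *Unlikely related* (first two items): "It does not follow a reasonable temporal sequence from administration of the drug", and a ready alternative cause.
- *Possibly related* ("must have first 2"), introduced as covering events "felt unlikely to be related to the administration of the study drug, but the possibility cannot be ruled out with certainty": plausible timing, and "It could readily have been a result of the patient's clinical state, environmental or toxic factors" or other therapy.
- *Probably related* (first three items): plausible timing, no reasonable alternative explanation, and "It disappears or decreases upon cessation of drug or reduction in dose".
- *Related* (first three items): as for *probably related*, with recurrence on rechallenge. Measured drug levels may stand in for timing.

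A footnote to the dechallenge items allows exceptions when an event persists after the drug is stopped but is clearly drug-related.

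**The concern.** The alternative-cause item works in opposite directions in neighbouring categories. *Possibly related* demands an alternative cause. The two stronger categories demand its absence, but also demand a favourable dechallenge. An event for which the drug is the only explanation, and for which no dechallenge result is available, falls between them.

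The ordering is also inverted. Adding a competing cause, which weakens the case against the drug, moves the event into *possibly related* and through the Section 6.8.3 gate.

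Two uses of the scale are still live: the Phase 2a tolerability trigger, which acts on a small count, and the related-AE summaries in the final report. The table also conflicts with the reasonable-possibility standard in Section 10.3.1, so two sites following different parts of the protocol could rate the same event differently.

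**Working it through.** The plan states no figure that depends on Table 13, so there is nothing to reproduce. The check is one of logic, followed by the arithmetic of the trigger.

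**Step 1. Enumerate the compulsory items.** Each combination of timing, alternative cause, dechallenge and rechallenge was set against the table, leaving aside the drug-level substitute for timing under *related*.

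| Timing plausible | Alternative cause | Dechallenge | Category met |
|---|---|---|---|
| yes | yes | any result or none | possibly related |
| yes | no | improved, recurred on rechallenge | probably related and related |
| yes | no | improved, no positive rechallenge | probably related |
| yes | no | persisted | none on the compulsory items; probably related or related through the footnote if relatedness is clear |
| yes | no | not done, not yet known or not assessable | **none, with or without the footnote** |
| no | yes | any result or none | unlikely related |
| no | no | any result or none | none |

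*Unrelated* cannot absorb the bold row, because it needs a clear extraneous cause and there is none. Comparing that row with the first shows the inversion: only the competing cause differs. The last row is also unassigned, but without plausible timing there is little reason to expect such an event to count as a DLT.

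**Step 2. Trace the bold row to the decision.** An event with no category has not been rated possibly related, probably related or related. It therefore misses the main route in Section 6.8.3 and can count only through the discretionary clause.

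**Step 3. Size at the Phase 2a trigger.** For a 15-patient cohort, 0.333 × 15 = 4.995, so the trigger is reached at 5 DLTs. One event separates 4/15 = 26.7% from 5/15 = 33.3%. For the planned 30-patient mTNBC cohort, 0.333 × 30 = 9.99, and one event separates 9/30 = 30.0% from 10/30 = 33.3%.

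**Step 4. Sensitivity, on assumed inputs only.** Suppose a share f of true Cycle 1 DLTs falls in the gap and the discretionary clause recovers none of them. With true rate p, the counted rate is p(1 − f), and the chance of reaching the trigger is P(X ≥ 5) for X ~ Binomial(15, p(1 − f)):

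| True rate p | f = 0 | f = 10% | f = 25% | f = 50% |
|---|---|---|---|---|
| 33.3% | 59.5% | 48.3% | 31.3% | 8.9% |
| 40% | 78.3% | 67.8% | 48.5% | 16.4% |
| 50% | 94.1% | 88.0% | 72.0% | 31.4% |

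The documents give neither p nor f. The table shows how the trigger would respond, not how it has behaved.

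**The case against.** Several points on the other side have force.

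- **Section 10.3.1 already allows for missing dechallenge data.** This shows the intent. But the same bullet sends the investigator to the table, whose compulsory items say otherwise. What remains is a conflict to reconcile.
- **The DLT gate is not absolute.** A reader might infer that Section 6.8.3 shuts such an event out. It does not: the discretionary clause can admit it. That leaves the event without a category and makes its counting a case-by-case matter.
- **Dechallenge can be seen in Cycle 1.** A reader might infer that a single-infusion cycle makes dechallenge unobservable. The item accepts stopping the drug, and after Day 1 no further dose is due for 21 days. Improvement in that time can reasonably be read as dechallenge, although the table does not say so. The footnote covers persistent events that are clearly related. The residue is events judged before their course is known, events whose course cannot be assessed, and persistent events without clear relatedness.
- **The shared wording does not create overlap.** Both *unlikely related* and *possibly related* are described as unlikely to be drug-related, and a reader might infer that one event could be placed in either. The compulsory timing items are opposites, so it could not.
- **No harm is shown.** A reader might infer that the MTD is in doubt. Section 2.6 reports two Cycle 1 DLTs at 270 mg/m² and none in six patients at 220 mg/m², and the dose has been set. Treatment-related AEs were recorded in 21 of 24 Phase 1a patients and in 10 of 13 Phase 2a patients. No visible passage shows an event lost to the gap.
- **One event can tip any threshold.** This is true. The 4/15 versus 5/15 comparison shows sensitivity, not frequency.

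**Conclusion.** The point holds in a limited form. Read as a checklist, Table 13 gives no category to an event with plausible timing, no alternative cause, and dechallenge not done, not yet known or not assessable. It ranks that event below one with a competing explanation, and it disagrees with Section 10.3.1. This is a stated rule that gives a wrong result, not a missing detail.

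The consequence is modest. Such an event can reach the Phase 2a trigger only through the discretionary clause, and it may be absent from the related-AE tables. One event can decide the trigger in a 15-patient cohort, but the documents do not say how often the gap would arise. The conclusion assumes that investigators apply the compulsory items literally; where they rely on Section 10.3.1 instead, the gap may never show. It gives no ground for reopening the Phase 1a dose decision.

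**What to change.** In Appendix E, Table 13:

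1. Under *possibly related*, keep plausible timing compulsory and make the alternative-cause item optional: such a cause may be present but need not be.
2. State that unavailable dechallenge or rechallenge information does not place an event below *possibly related*, in line with Section 10.3.1.
3. As tidying only, reword the description of *possibly related* so that it no longer calls the event unlikely to be drug-related.

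The eCRF completion guidance should carry the same wording. Events with a clear extraneous cause stay *unrelated*, which limits over-inclusion.

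The cost is a wording change to one appendix table and the guide, and a few more events may be classed as related. Because the change comes mid-trial, events already assessed should be checked against the revised wording before Phase 1a and Phase 2a data at the same dose are summarized together under Section 14.1. Otherwise those summaries would mix two definitions of relatedness.
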